**Study Name:** **Kera Sol Post-LASIK: A Benefit Study**

**Objective:** To evaluate the influence of Kera Sol tear usage during the initial two-week postoperative period after LASIK has on the signs and symptoms of STODS.

**Background:** Laser-Assisted In Situ Keratomileusis (LASIK) is a common and effective refractive surgery that reshapes the cornea to correct vision problems. However, a frequent temporary side effect post-surgery is dry eye. This occurs because the LASIK procedure can disrupt the corneal nerves responsible for signaling tear production and can also affect the goblet cells in the conjunctiva that contribute to the tear film's stability. This neurotrophic effect and potential disruption of the ocular surface lead to reduced tear production, increased tear evaporation, and an unstable tear film. Given the prevalence of post-LASIK dry eye and the established benefits of artificial tears in managing this condition, there is an ongoing need to explore formulations that may offer enhanced or more targeted relief. Kera Sol tears, presumably a specific formulation of artificial tears, may offer unique benefits due to its specific composition.

**Study Design:** Prospective, single-site, two-arm randomized study evaluating the impact of Kera Sol tears on the signs and symptoms of STODS in 60 patients who underwent bilateral LASIK. Both groups will be prescribed the standard of care post-operative prescription combination steroid and antibiotic drop. Additionally, subjects will be randomized to administer the study drop (Kera Sol) dosed QID for 14 days.

The primary endpoints, assessed using descriptive analysis, will be the change from baseline corneal staining on the 0-15 NEI scale and the change from baseline discomfort score on the UNC DEMS questionnaire to Day 14. Additional endpoints measured will include uncorrected visual acuity (UCVA), BEDx score and best-corrected visual acuity (BCVA) at 1 week, and residual refractive error at Day 14.

**Subject Population:** 60 subjects, who have scheduled for LASIK in both eyes, will be enrolled.

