## Procedures

Subjects will be recruited from the site's current patient population who have been scheduled and underwent bilateral LASIK procedure. Enrollment and informed consent will be administered by study coordinators. Data will be collected by investigators and study coordinators as follows. Data may be carried from standard of care visits within 90 days of Visit one.

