### **Visit 1 (pre-op):**

- Informed consent will be obtained prior to collection of any data
- Each subjects' demographics, medical, and concomitant medications will be reviewed.
- Inclusion and exclusion criteria will be reviewed for each subject.
- University North Carolina Dry Eye Management Scale (UNC DEMS) questionnaire will be administered
- Concomitant medications will be reviewed.

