### **Visit 2 (1 day post-op):**

- Randomization will occur
- Daily topical artificial tear and study drop log will be provided

- University North Carolina Dry Eye Management Scale (UNC DEMS) questionnaire will be administered
- Monocular and binocular uncorrected distance visual acuity (UDVA) will be obtained on an ETDRS chart at a distance of 20 feet
- 25% low contrast sensitivity will be measured using the Pelli-Robson chart
- Slit lamp examination will be performed
- Corneal fluorescein staining will be obtained using the BEDx software
- Adverse events will be collected

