## **Data Analysis and Data Monitoring**

Data will be captured by the principal investigators, sub-investigators and study coordinators. Data will be documented on source documents and subjects will be identified as subject numbers.

Data analysis will occur on an excel spreadsheet or in R statistical software with subjects identified as a subject number. The Excel spreadsheet or R scripts will be on computer(s) that are password protected.

Baseline demographic and ocular characteristics will be quantified using descriptive statistics. Statistical analysis will be completed on all primary and secondary endpoints.

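### The primary endpoints are fixed as descriptively assessed change from baseline, and nothing in the protocol commits to the difference between the randomized arms

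*Protocol*

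**What the plan says.** The Study Design section describes a "two-arm randomized study evaluating the impact of Kera Sol tears on the signs and symptoms of STODS" in 60 subjects having bilateral LASIK. It fixes how the main results are assessed: "The primary endpoints, assessed using descriptive analysis, will be the change from baseline corneal staining" (0-15 NEI scale), together with the change in UNC DEMS discomfort to Day 14.

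The Data Analysis and Data Monitoring section uses different words. For baseline data: "Baseline demographic and ocular characteristics will be quantified using descriptive statistics". For the endpoints: "Statistical analysis will be completed on all primary and secondary endpoints". It does not say what that analysis is.

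Three other statements bear on the point:

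- The Background says that "a frequent temporary side effect post-surgery is dry eye", and Study Design gives both groups the same steroid and antibiotic drop.
- For the symptom score, Visit 1 (pre-op) states "University North Carolina Dry Eye Management Scale (UNC DEMS) questionnaire will be administered", and the questionnaire is listed again at Visit 2. Visit 1 lists no staining; Visit 2, one day after surgery, is the first to do so: "Corneal fluorescein staining will be obtained using the BEDx software". Randomization is also at Visit 2.
- Procedures adds: "Data may be carried from standard of care visits within 90 days of Visit one". No section says which visit is the baseline.

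**The concern.** Randomization buys one thing, which is a comparison of arms that differ only by allocation. The protocol's single statement about assessing its primary endpoints does not name that comparison. An analyst following Study Design could report the mean change in each arm and stop. One following the Data Analysis section could test between arms. Both could claim to have followed the protocol.

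The gap matters more here than in a stable condition. From a postoperative baseline, both arms may improve simply because the eye recovers. From a preoperative baseline, both arms carry the effect of surgery. In either case change within the Kera Sol arm mixes the drop's effect with something that also happens without it. At stake is whether a reader can attribute any reported benefit to the drop.

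**Working it through.** **Text check.** The Objective, Study Design, visit schedules and Data Analysis section contain no between-arm estimate, interval or hypothesis for either primary endpoint. The nearest wording is the design phrase quoted above, which implies a comparison but does not commit the analysis to one. The protocol also gives no alpha, power, effect size, SD, allocation ratio or dropout, so it has no figure of its own to reproduce.

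**Precision of the contrast that should be reported.** From the protocol: 60 subjects, two arms. Assumed: 1:1 allocation, one value per subject, equal SDs in the two arms.

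Unadjusted 95% CI half-width, in SDs of change: t(0.975, n1+n2-2) × √(1/n1 + 1/n2).

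- 30 and 30: 2.002 × 0.2582 = 0.517
- 27 and 27 (10% dropout, assumed): 0.546

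Adjusted for baseline, let k be the Day 14 SD divided by the baseline SD, and ρ the correlation between baseline and Day 14. In units of the baseline SD, the residual SD is k√(1-ρ²) and the SD of change is √(1+k²-2ρk). The half-width in SDs of change is

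t(0.975, 57) × 0.2582 × k√(1-ρ²) / √(1+k²-2ρk).

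Assumed ranges: ρ 0.3 to 0.7, k 0.5 to 1.5.

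| k | ρ = 0.3 | ρ = 0.5 | ρ = 0.7 |
|---|---|---|---|
| 0.5 | 0.253 | 0.259 | 0.249 |
| 1.0 | 0.417 | 0.448 | 0.477 |
| 1.5 | 0.483 | 0.508 | 0.516 |

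Worked cell (k = 0.5, ρ = 0.3): 0.517 × 0.5 × 0.954 / 0.975 = 0.253. The gain vanishes as ρk approaches 1, because the change score is then already close to the best adjustment (k = 1.5, ρ = 0.7 gives ρk = 1.05). The range is therefore about 0.25 to 0.52.

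**Illustration of a possible misreading, not of a planned analysis.** Suppose the drop has no effect, the baseline is postoperative, and both arms recover by m SDs of change (m is assumed; the protocol gives no value). If someone put a 95% CI on the change in the Kera Sol arm alone (n = 30), the chance that it excludes zero on the side of improvement is P(noncentral t, 29 df, ncp m√30 > 2.045).

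- m = 0.3: 0.355
- m = 0.5: 0.754
- m = 0.8: 0.988

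The between-arm interval would exclude zero in favour of Kera Sol 2.5% of the time in each case.

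**Baseline.** The visit lists allow UNC DEMS a baseline at Visit 1 or Visit 2, and list staining first at Visit 2. The two primary endpoints could therefore be measured from opposite sides of surgery. Visit 2 carries both measures.

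**The case against.** The strongest reply is that a descriptive analysis is a legitimate choice for a study of 60 with no stated hypothesis, that it can include the between-arm difference, and that comparing arms is the ordinary reading of a two-arm randomized design. The model, covariates and interval would normally be set in an SAP, which may exist. Much of this is fair. A descriptive primary analysis is not in itself an error, and the absence of a test or model is no finding. What remains is that the protocol does state how the primary endpoints are assessed, and that statement does not name the contrast.

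Three stronger readings are tempting, and the document does not support them.

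- *The two sections contradict each other.* Descriptive statistics are a form of statistical analysis, and the Data Analysis section does not say that they are for baseline data only. Both sentences can be true together. This is ambiguity to be resolved.
- *The trial plans a within-arm test that will usually mislead.* No within-arm interval or test is planned. The 36%, 75% and 99% in the illustration depend on an assumed recovery and a postoperative baseline. From a preoperative baseline, both arms might worsen and no false improvement would appear.
- *The unsettled baseline biases the comparison.* If the baseline is defined identically in both arms, its side of surgery affects interpretation and precision but does not bias the randomized contrast. Nor does the Procedures sentence say that carried data may serve as an endpoint baseline. This part is secondary.

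Adjustment for baseline is also an improvement and not a necessity. An unadjusted difference in change would meet the main complaint.

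**Conclusion.** The point holds in a limited form. The protocol leaves its primary analysis ambiguous between two sections and commits to the between-arm difference in neither. In a condition it calls temporary, with the same background drop in both groups, by-arm change alone could satisfy Study Design and still not answer the Objective. This should be fixed because the remedy is nearly free, not because a wrong analysis has been planned.

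Assuming 30 per arm, the contrast would carry a 95% half-width of about 0.52 SD of change unadjusted, or 0.55 with 10% dropout. With adjustment it is about 0.25 to 0.52 SD over the assumed correlations and SD ratios. The half-widths show what the study can estimate; they do not measure the harm done by the wording. Confidence is medium, since an SAP may already supply the contrast.

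**What to change.** In Study Design, replace the descriptive-analysis qualifier on the primary endpoints with wording such as:

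> each summarised as the between-arm difference at Day 14, adjusted for the baseline value, with a 95% CI, as estimation and not confirmatory

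Keep by-arm mean changes as supporting description, and bring the endpoint sentence in Data Analysis and Data Monitoring into line with this.

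Name one baseline visit for both primary endpoints, with values taken before the first study drop and defined identically in both arms. Visit 2 is available, since randomization, staining and UNC DEMS all occur there. Say whether a value carried from a standard-of-care visit may serve as baseline.

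The cost is three or four sentences and a few lines of R, with no added visits, data or subjects. The downside is that the interval will be wide at this sample size, and the result may look less favourable than an improvement within one arm.

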## Materials and Methods

- Informed consent will be obtained prior to collection of any data.
- Each subjects' demographics, medical history, will be reviewed.
- Inclusion and exclusion criteria will be reviewed for each subject.
- Subjects will be asked to report their daily use of study drop
- Subjects will be asked to report their dry eye symptoms using the developed University North Carolina Dry Eye Management Scale (UNC DEMS) scale
- Each subjects' monocular and binocular uncorrected distance visual acuity (UDVA) will be obtained on an ETDRS chart at a distance of 20 feet
- A manifest refraction will be performed on each subject.
- Monocular and binocular best corrected distance visual acuity (BCDVA) will be obtained on an ETDRS chart at a distance of 20 feet in photopic lighting conditions.
- 25% low contrast sensitivity will be evaluated using a Pelli-Robson chart.
- The subjects' eyes will be thoroughly examined at the slit lamp.
- Corneal fluorescein staining will be evaluated using the BEDx software
- Intraocular pressure will be obtained using clinical standard of care

### **Inclusion criteria:**

1. Be willing and able to sign the informed consent form (ICF)
2. Be at least 18 years of age at the screening visit
3. Be undergoing LASIK treatment in both eyes
4. Be literate and able to complete questionnaires independently
5. Be able and willing to use the study drug and participate in all study assessments and visits
6. Have provided verbal and written informed consent

### **General Exclusion criteria:**

1. Use of topical prescription dry eye medications such as lifitegrast, cyclosporine, loltolaner, etc.

2. Have a break in the integrity of the corneal epithelium such as a persistent corneal epithelial defect, or corneal ulcer.
3. Have presence of corneal pathology that may interfere with LASIK outcomes
4. Active infectious, ocular or systemic disease
5. Have a history of ocular inflammation or macular edema
6. Have had clinically significant active infectious keratitis in the past 3 months
7. Have history of prior refractive surgery
8. Have placement of temporary punctal plugs in the past 1 month or current presence of permanent punctal plugs at time of screening
9. Patients with usual relative and absolute contraindications for LASIK surgery (Patients with severe dry eye, recurrent corneal erosion, uncontrolled Glaucoma, collagen vascular disorders, keratoconus or signs of keratoconus, uncontrolled Diabetes, Herpes)
10. Autoimmune or immunodeficiency diseases
11. Pregnant or nursing women
12. Patients with history of previous ocular surgery

## Procedures

Subjects will be recruited from the site's current patient population who have been scheduled and underwent bilateral LASIK procedure. Enrollment and informed consent will be administered by study coordinators. Data will be collected by investigators and study coordinators as follows. Data may be carried from standard of care visits within 90 days of Visit one.

### **Visit 1 (pre-op):**

- Informed consent will be obtained prior to collection of any data
- Each subjects' demographics, medical, and concomitant medications will be reviewed.
- Inclusion and exclusion criteria will be reviewed for each subject.
- University North Carolina Dry Eye Management Scale (UNC DEMS) questionnaire will be administered
- Concomitant medications will be reviewed.

### **Visit 2 (1 day post-op):**

- Randomization will occur
- Daily topical artificial tear and study drop log will be provided

- University North Carolina Dry Eye Management Scale (UNC DEMS) questionnaire will be administered
- Monocular and binocular uncorrected distance visual acuity (UDVA) will be obtained on an ETDRS chart at a distance of 20 feet
- 25% low contrast sensitivity will be measured using the Pelli-Robson chart
- Slit lamp examination will be performed
- Corneal fluorescein staining will be obtained using the BEDx software
- Adverse events will be collected

**Visit 3 (7 +/-2 days post-op):**

- Daily topical artificial tear and study drop log will be provided
- University North Carolina Dry Eye Management Scale (UNC DEMS) questionnaire will be administered
- Monocular and binocular uncorrected distance visual acuity (UDVA) will be obtained on an ETDRS chart at a distance of 20 feet
- Manifest refraction will be performed
- Monocular and binocular best corrected distance visual acuity (BCDVA) will be obtained on an ETDRS chart at a distance of 20 feet
- 25% low contrast sensitivity will be measured using the Pelli-Robson chart
- Slit lamp examination will be performed
- Corneal fluorescein staining will be obtained using the BEDx software
- Adverse events will be collected

**Visit 4 (14 +/-2 days post-op):**

- Daily topical artificial tear and study drop log will be provided
- University North Carolina Dry Eye Management Scale (UNC DEMS) questionnaire will be administered
- Monocular and binocular uncorrected distance visual acuity (UDVA) will be obtained on an ETDRS chart at a distance of 20 feet
- Manifest refraction will be performed
- Monocular and binocular best corrected distance visual acuity (BCDVA) will be obtained on an ETDRS chart at a distance of 20 feet
- 25% low contrast sensitivity will be measured using the Pelli-Robson chart
- Slit lamp examination will be performed
- Corneal fluorescein staining will be obtained using the BEDx software
- Intraocular pressure will be measured per standard of clinical care
- Adverse events will be collected

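### Kera Sol stops after a fixed 14 days, but the visit that supplies the Day 14 primary values may fall as late as Day 16, so some compliant treated subjects can be assessed off drop

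*Protocol*

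**What the plan says.** All references are to the Protocol.

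- **Course.** Study Design: "subjects will be randomized to administer the study drop (Kera Sol) dosed QID for 14 days".
- **Common treatment.** "Both groups will be prescribed the standard of care post-operative prescription combination steroid and antibiotic drop". No study drop is named for the other arm.
- **Endpoints.** The two primary endpoints are change from baseline in corneal staining and "the change from baseline discomfort score on the UNC DEMS questionnaire to Day 14". They are to be summarized descriptively ("The primary endpoints, assessed using descriptive analysis").
- **Objective.** It concerns "Kera Sol tear usage during the initial two-week postoperative period".
- **Start.** Under Visit 2, one day after surgery: "Randomization will occur". The day of the first dose is not stated.
- **Visits.** The later visits are headed "Visit 3 (7 +/-2 days post-op" and "Visit 4 (14 +/-2 days post-op", that is, Days 5 to 9 and Days 12 to 16.
- **Log.** A daily log covering artificial tears and the study drop is listed at Visits 2, 3 and 4. No text instructs subjects to continue the drop until Visit 4, or requires that visit to take place while they are still dosing.

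**The concern.** A symmetric two-day window is routine in itself. The difficulty is pairing it with a stopping day that does not depend on the visit. A subject who follows the protocol exactly can finish the course and be examined a day or two later, while another is examined in the middle of dosing. Both results enter the summary as Day 14 values.

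On the text as written, the end of the course changes treatment in the Kera Sol arm only, because the steroid and antibiotic drop is shared and the other arm has no named study drop. If part of the benefit of a tear drop lasts only while it is in use, values from treated subjects seen late would understate the on-treatment effect, with no matching shift in the other arm. Since the primary analysis is descriptive, the stake is the clarity and size of the observed difference and not the power of a test.

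**Working it through.** The protocol states no figure on this point, so there is none to reproduce. The check is a day count, followed by an illustration in hours.

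**1. Which visit supplies the Day 14 values.** Visit 3: 7 − 2 = Day 5 to 7 + 2 = Day 9. Visit 4: 14 − 2 = Day 12 to 14 + 2 = Day 16. Only Visit 4 contains Day 14.

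**2. Last dosing day, counting calendar days.** A 14-day course begun on Day s ends on Day s + 13. Randomization on Day 1 makes s = 1 the earliest start; s = 2 is an assumption.

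| First dose | Last dosing day | Permitted visit days after the course |
|---|---|---|
| Day 1 | 1 + 13 = Day 14 | Days 15 and 16 (2 of 5) |
| Day 2 | 2 + 13 = Day 15 | Day 16 (1 of 5) |

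**3. Counting doses instead.** Fourteen days at four a day is 14 × 4 = 56 doses. If k doses are taken on Day 1 and four on each of Days 2 to 14 (13 × 4 = 52), then 56 − k − 52 = 4 − k doses remain for Day 15. For k = 1, 2 or 3, Day 15 is still a dosing day and only Day 16 is after the course. For k = 4 the course ends on Day 14.

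If a partial first day and a Day 2 start are combined, the same sum puts the remaining 4 − k doses on Day 16, and no permitted visit day lies wholly after the course.

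**4. Hours since the last drop.** Assumed, not in the protocol: last drop of the day at 20:00 to 22:00, and clinic from 08:00 to 17:00. For the 56-dose count, drops are assumed at 08:00, 12:00, 16:00 and 20:00.

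- Ordinary overnight gap during use: 22:00 to 08:00 = 10 h; 20:00 to 08:00 = 12 h.
- Day 1 start, Day 15 visit: 24 + 8 − 22 = 10 h to 24 + 17 − 20 = 21 h.
- Day 1 start, Day 16 visit: 48 + 8 − 22 = 34 h to 48 + 17 − 20 = 45 h.
- Day 2 start, Day 16 visit: 10 to 21 h, by the same sum as the Day 15 visit above.
- 56 doses with a partial Day 1, Day 16 visit: last drop on Day 15 at 16:00, 12:00 or 08:00 for k = 1, 2, 3, giving 16–25, 20–29 or 24–33 h. A Day 15 visit is then at most 1, 5 or 9 h after the last drop, within the ordinary gap.

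An early Day 15 visit therefore hardly differs from on-course use. The clearest contrast is Day 16 after a Day 1 start.

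**5. Exposure by the visit, with and without the change proposed below (Day 1 start).**

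| Visit day | 12 | 13 | 14 | 15 | 16 |
|---|---|---|---|---|---|
| Dosing days, current text | 12 | 13 | 14 | 14 | 14 |
| Dosing days, drop continued to the visit | 12 | 13 | 14 | 15 | 16 |

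With the change, course length is max(14, visit day − s + 1): 14 to 16 days for s = 1 and 14 to 15 days for s = 2.

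**The case against.** The strongest reply is that the objective concerns two weeks of use, and a subject who completes those two weeks and is seen a day or two later has had exactly that exposure. Nothing in the protocol demands assessment on drop. This stands as far as it goes: such a subject still informs the objective, so the point is an improvement and not an error.

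Several narrower points also stand:

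- No harm is demonstrated. The protocol gives neither the share of late visits nor how fast an effect fades, and the hours above rest on assumed clock times.
- With a Day 2 start, a partial first day and a 56-dose count together, even Day 16 is a dosing day. That is a remote reading, but the unstated first-dose day leaves it open.
- It is not certain that only one arm changes state. The duration of the steroid and antibiotic drop is not given, and because the log also covers other artificial tears, off course need not mean untreated.
- The protocol states no recall period for the UNC DEMS. If answers look back over several days, a late score would still largely reflect days on drop.
- Continuing the drop to the visit widens the range of dosing days from 12–14 to 12–16.

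The argument that an analysis plan could deal with this is weaker. Visit dates and the log would let an analyst flag late values, but no analysis can put a subject back on drop. When to stop dosing is an instruction for the protocol.

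**Conclusion.** The point holds as a minor design improvement. With a Day 1 start and calendar-day dosing, a fully compliant Kera Sol subject seen on Day 15 or 16 gives the primary values after treatment has ended. With a Day 2 start in calendar days, or a Day 1 start with a partial first day counted as 56 doses, this is true of Day 16 only.

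Any dilution depends on how many visits fall late and how quickly an effect fades. Neither is given, so no effect size can be attached and it may be zero. No loss of power is claimed, and the comparison remains valid. Confidence is medium, mainly because the first-dose day and the meaning of the 14-day course are not fixed.

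**What to change.** In Study Design, state that Kera Sol is used four times daily for 14 days or until the Visit 4 assessments are complete, whichever is later. Subjects seen late within the window then stay on drop until they are examined, whichever start day or dose count applies.

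The cost is that one line plus a small supply margin: with a Day 1 start, up to 2 extra days × 4 = 8 doses per eye; with a Day 2 start, 1 × 4 = 4 doses per eye. It is needed only for late visits. The price is a course of variable length that can run up to two days past Day 14, slightly beyond the two weeks in the objective.

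If the sponsor prefers to keep the course at exactly 14 days, the alternative is to close the late side of the Visit 4 window at Day 14, at the cost of less room for scheduling.
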